3.2.3 Non-compliance corrected (ITT) population

An adjustment for lack of Cytosponge™ use in the intervention arm (non-compliance) will be made following the method detailed in Cuzick et al., which gives an estimate of the effect of the intervention for those who attend the Cytosponge™ test invitation. This will show the causal impact of the Cytosponge™ on BE detection.

BE detection in compliers in the intervention arm will be compared to BE detection in potential compliers in the usual care, i.e. participants who would have received the test if they had been offered it. In order to do that, the proportions of actual or potential compliers/non-compliers in the two arms is assumed to be the same, and so is the proportion of BE detection in actual or potential non-compliers. The proportion of BE detection in potential compliers in the usual care arm will be estimated as:

$$\frac{\text{no. BEs in usual care} - \text{no. BEs in potential non compliers}}{\text{no. potential compliers}}$$

Data on number of BEs detected in the two study arms will come from the ITT analysis on the primary endpoint.

The relative protection given by the intervention in those who comply is to be estimated as

$$\frac{S_{11}/N_1}{S_0/N_0 - S_{10}/N_1}$$

where $\{S_0, S_{10}, S_{11}\}$ and $\{N_0, N_{10}, N_{11}\}$ are the numbers of BE detected and the numbers of individuals in the usual care arm, in the non-complier population (intervention) and in the complier population (intervention), respectively.

Note: in order to obtain an estimate of the non-compliance corrected effect, data from the CLR group will be treated in the same way as data from the PLR group, i.e. the two datasets will be merged and the effect of clustering in the CLR group will not be considered. However, in order to obtain confidence intervals for the effect, the variance inflation factor for the study as a whole will be applied to the variance of the effect that ignores the clustering. It is noted that this method assumes that the compliance within cluster is independent of the BE prevalence within cluster. New methodology to better adjust for the clustering may be developed.

3.2.4 Safety population

The safety analysis will look at all participants attempting to swallow a Cytosponge™: both the ones producing a Cytosponge™ sample ('successful swallows'), independently from the test result, and the ones not able to swallow a sponge. The endpoints related to the safety of the Cytosponge™, i.e. total number of AEs, number of AEs per participant, number/proportion of participants experiencing an AE, will be analysed on this population.

3.3 Subgroup definitions

Primary endpoint analysis will be carried out separately for the CLR and PLR groups as asked by the Medicines and Healthcare products Regulatory Agency (MHRA) in a communication on 31 May 2018. If the results from both subgroups favour the study intervention, i.e. the proportion of participants with diagnosed BE is greater (regardless of the level of significance) in the invitation to the Cytosponge™ arm than in the usual-care arm, then a combined analysis shall be performed.

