2.5.4 Variable follow-up periods

Because of delays in the implementation of the change of study design (from CLR to CLR with additional PLR group), it was decided that participants/practices could have

a follow-up longer than 12 months to compensate for participants/practices who will have a follow-up shorter than 12 months due to time constraints.

Different practices will have different follow-ups as long as the **weighted average follow-up** for the study will be greater than 12 months, as shown by the following formula:

$$\text{avg}_{\text{FU}} = \frac{\sum_{i=1}^P F_i M_i + \sum_{j=1}^Q F_j N_j}{\sum_{i=1}^P M_i + \sum_{j=1}^Q N_j} \geq 12$$

where F_i, F_j are the different lengths of follow-up (in months) for each different group, M_i are the numbers of patients with different follow-ups in the CLR group in 'equivalent size' terms, N_j are the numbers of patients with different follow-ups in the PLR group, $\sum_{i=1}^P M_i$ is the total size (in 'equivalent' terms) of the CLR group, and $\sum_{j=1}^Q N_j$ is the total size of the PLR group.

According to our current projections, all practices will have between 8 and 18 months of follow-up. The end date of follow-up will be when a site performs their local coded search; it will therefore be taken from the Coded Search case report form (CRF).

Note: in case a weighted average follow-up of 12 months or more could not be guaranteed, the power of the study would be less than 90%. The following table illustrates the potential loss in power with shorter follow-up:

Total average follow-up (months)	Factor by which to inflate sample size
9	1.24
9.5	1.18
10	1.13
10.5	1.09
11	1.06
11.5	1.03

A detailed explanation on how to calculate the factors by which to inflate the sample size is available here:

[G:\EMS\CPTU\BEST3\Section 26 STATISTICS\26.3 Power calculations\Sample size \(following Amendment 6\)\BEST3_Sample size.pdf](G:\EMS\CPTU\BEST3\Section 26 STATISTICS\26.3 Power calculations\Sample size (following Amendment 6)\BEST3_Sample size.pdf)

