7.1 Method for analysis of endpoints

7.1.1 Analysis of primary endpoint

The power under various assumptions regarding sensitivity, BE prevalence and intra-class correlation will be calculated based on the actual numbers recruited, the uptake observed and the actual duration of follow-up.

Null Hypothesis: The BE detection rate at 12 months (excluding any found on random exit endoscopies) is the same in the intervention arm and the control (usual care) arm.

Alternative hypothesis: The BE detection rate at 12 months is greater in the intervention arm than in the control (usual care) arm.

The CLR and PLR group will be first analysed separately; if the results from the two parts of the study favour the test, a combined analysis will be performed.

Primary endpoint data will be collected according to the methods explained in Section 2.3. This aims at guaranteeing an equal approach to data collection in the two study arms, but implies that, for the primary endpoint analysis, we will only consider BEs that were ascertained systematically through one of the three methods.

Sites have variable follow-ups. The number of person-years of follow-up will be calculated by taking as the end date the date of the local coded search in a practice and as start date the date the first letter of introduction to the study was sent plus 15 days. Follow-up will be considered until whichever is first: diagnosis of BE, the date of the systematic search for BE, the day before a research endoscopy. BE found on research endoscopy will not be counted towards the primary endpoint.

Rates will be calculated out of 1000 person-years. A single rate will be calculated during follow-up in the control arm. Two rates will be calculated in the intervention arm: the rate within four months of randomisation and the rate beyond four months from randomisation. In order to estimate the average rate within 12 months of randomisation in the intervention arm, a weighted average of these two rates will be taken with weights 2:1.

The methods mentioned in the sections below are taken from:

Hayes RJ and Moulton LH. (2009). *Cluster randomised trials*. ed. Boca Raton, FL: Chapman & Hall/CRC, pp. 178-9.

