7.1.1.1 Unadjusted analysis

CLR group

The CLR group is stratified by cluster size, i.e. number of participants per practice, as per the categories defined in the Milestone 1 review of the sample size (see Section 2.5.2): 50-65, 66-90, 91-125, 126-175, 176-225.

As a primary analysis, we will run a regression analysis based on individual-level data, followed by a secondary analysis based on cluster-level summaries to ensure that the conclusions are robust.

We will report on number of clusters and patients by stratum and study arm, and on the weighted average follow-up for the CLR group as shown in Section 2.5.4.

Individual-level data

We will first report on cumulative BE detection rate at one year (/ 1000 person-years) by stratum and study arm, and overall, using individual-level data. The one-year rate in the intervention arm will be estimated assuming a constant rate in the first four months and a (possibly different) constant rate thereafter (up to 18 months).

Primary endpoint data will be analysed by a mixed-effects Poisson regression for BE with fixed effects for the treatment and random effects to account for between-cluster variation (i.e. a random effect for the level of BE in each GP practice), with the number of person-years of follow-up as the offset. Additional fixed effect parameters will be included to account for strata (size of clusters in each stratum: 50-65, 66-90, 91-125, 126-175, 176-225).

The resulting 12-month rate ratio will be reported with 95% confidence interval and will be formally tested to see if it is significantly greater than 1.0 (with a two-sided alpha of 0.05).

To fit the Poisson regression random effects model to data, we will model the random effects using a log-gamma distribution.

In Stata, the `mepoisson` command performs a mixed-effects Poisson regression. See Section 11.2.1.1 of Hayes and Moulton for an explanation on the method. There will be two observations (and two durations of follow-up) for each patient: one for the first four months and a second thereafter. There will be a separate treatment effect for each period. The overall treatment effect will be calculated as the weighted mean of the two treatment effects using the Stata command `nlcom`.

Cluster-level data

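### Section 3.3 decides on the combined analysis by comparing proportions with BE, but each group's primary result is a person-time rate ratio, and in the CLR group the two can differ in direction

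*SAP*

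**What the plan says.** SAP 3.3 asks for separate CLR and PLR analyses of the primary endpoint. It allows a combined analysis only if both favour the intervention, and spells this out as "the proportion of participants with diagnosed BE is greater (regardless of the level of significance) in the invitation to the Cytosponge™ arm" than in usual care.

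SAP 7.1.1 repeats the condition without a statistic: "if the results from the two parts of the study favour the test, a combined analysis will be performed".

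The results themselves are specified in 7.1.1.1:
- **CLR group:** a mixed-effects Poisson model with a person-years offset, a practice random effect and two periods (first four months, then the rest). Size strata enter as well: "Additional fixed effect parameters will be included to account for strata". For the output, "The resulting 12-month rate ratio will be reported with 95% confidence interval".
- **PLR group:** a plain Poisson regression with a person-years offset, also reported as a rate ratio.

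On follow-up, 2.5.4 projects that "all practices will have between 8 and 18 months of follow-up". In the CLR group whole practices were randomised (2.5.5), so each practice and its follow-up belong to a single arm.

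**The concern.** The SAP treats follow-up as important enough for an offset, a two-period model and a check on weighted average follow-up. The condition in 3.3 uses none of this. A proportion rises with an arm's follow-up, and it gives full weight to a few practices with many BE cases. The CLR model allows for both.

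The requirement of 6764 individually randomised equivalents (2.5.2) is met only by the two groups together, so the condition decides whether the analysis the trial was sized for is run. As written, that analysis could be withheld although the reported CLR rate ratio is above 1, or run although it is below 1.

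**Working it through.** **1. The plan's own figure.** Intervention: 0.27 × (0.04 × 0.85 + 0.15 × 0.006) + 0.73 × 0.006 = 1.380%. Usual care: 0.1 × 0.06 = 0.6%. The two-proportion formula (pooled variance under the null, two-sided 5%, 90% power, no continuity correction) gives 3382 per arm, or 6764, as stated in 2.5.2.

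**2. How often the proportion itself has the wrong sign.** Normal approximation: difference 0.00780, pooled 2p̄(1 − p̄) = 0.0196.
- CLR, equivalent size 2120 (1060 per arm): SE = √(0.0196/1060) = 0.0043, z = 1.81, probability 3.5%.
- PLR, 5390 patients (2695 per arm): SE = √(0.0196/2695) = 0.0027, z = 2.89, probability 0.2%.

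The question therefore matters only for the CLR group.

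**3. What follow-up does alone.** At constant rates, the ratio of proportions is about the rate ratio times the ratio of mean follow-up. The two statistics disagree only when the rate ratio lies between 1 and the inverse of that follow-up ratio. Assume 72 equal practices (36 per arm) with follow-up uniform on 8–18 months. The SD is 10/√12 = 2.89 months. The SE of the difference in arm means is 2.89 × √(2/36) = 0.68 months, about 5% of the 13-month mean. Chance imbalance thus matters only when the rate ratio is close to 1. In simulation, follow-up alone gave about 0.6–2.2% disagreement (about 1% with 1:2 period weights). The rest comes from strata and practice effects.

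**4. Disagreement in sign between the proportion and the CLR model.** Simulated CLR trials used five size strata, practice effects and a strata-adjusted gamma-Poisson fit. The SAP does not give the number of CLR practices recruited; 60–72 is assumed.

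| Setting | Disagreement |
|---|---|
| ICC 0.025, 1.38% vs 0.6%; gamma, log-normal or beta practice effects; fixed or varying follow-up; single effect | 1.4–3.8% |
| Same, two periods, rates averaged 1:2 | 1.4–3.7% |
| Same, two periods, rates averaged 2:1 | 1.9–5.9% |
| ICC 0.025 held in each arm, 66–72 practices, 1.38%, 1:2 | 3.1–3.9% |
| Common gamma variance, 66–72 practices, early cases, 1.38%, 1:2 | 5.2–5.9% |
| Same, 72 practices, 2:1 | 7.0% |
| Same, 72 practices, 1.29% (24% uptake), 1:2 | 6.4–6.8% |
| ICC 0.01 | 0.4–2.5% |
| ICC 0.025, no effect, 1:2 | 13.5–14.6% |

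Much of the spread comes from how the ICC is turned into practice variance. Calibrated at 0.6%, the gamma variance is 0.025 × 0.994/0.006 = 4.14. Applied to the intervention arm at 1.38%, that implies an ICC of 0.0138 × 4.14/0.986 = 0.058, more than twice the assumed value.

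**5. Dependence on the averaging rule.** For the rates, 7.1.1 says "a weighted average of these two rates will be taken with weights 2:1", whereas periods of 4 and 8 months within a year are in the ratio 1:2. For the model, 7.1.1.1 says "The overall treatment effect will be calculated as the weighted mean of the two treatment effects", without naming the scale. One set of runs with 2:1 weights spanned 4.0–9.4%. Averaging log rate ratios 1:2 with early cases gave 14–20%. I leave these extremes outside the range because they arise from how the two periods are averaged, which is a separate matter.

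**6. Share withheld.** With 72 practices, 1.29%, ICC 0.025, common variance and 1:2 weights, the CLR part fails the condition in 9.9% of trials by proportion and 9.3% by rate ratio. Disagreement is 3.6% (withheld with a ratio above 1) plus 3.0% (passed with a ratio of 1 or less) = 6.6%. The two directions nearly cancel. With 2:1 weights they do not: almost all of the 7.0% is withholding with a ratio above 1.

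**The case against.** Several objections carry weight.

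- **Contradiction.** A reader might infer that 3.3 and 7.1.1 order opposite actions on the same data. They do not. Section 7.1.1 names no statistic and 3.3 holds the only definition, so the ordinary reading is that 3.3 governs. Nor does 3.3 call the proportion crude, and the clause may be loose wording for the model result. What stands is that the definition, as written, differs from the reported estimate.
- **Size.** A reader might take about 7% as the figure under the planned effect. Under 1:2 weights, values near 7% need the lower effect at 24% uptake together with the common variance, which inflates the ICC in the intervention arm. At 1.29% the proportion failed in 9.9% of those trials, against about 5% from the SAP's equivalent size (0.0069/0.0042 = 1.65 SE). At the planned effect with ICC 0.025 in each arm, disagreement is 3–4%.
- **Novelty.** It would be wrong to say that the SAP does not otherwise use proportions. Section 2.5.2 sizes the trial on them, and 3.2.3 uses them for the compliance-corrected effect.
- **Gain.** The share withheld hardly changes with 1:2 weights and a common variance, so the change should not be presented as a rescue of power.
- **Cost.** A proportion can always be computed, whereas the 12-month rate ratio rests on weights and a scale not yet settled. The MHRA communication is not available here, so whether the wording of the condition came from it is unknown.

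**Conclusion.** The mismatch holds and is minor. Section 3.3 lets a proportion decide whether the combined analysis is run, while the results it stands for are person-time rate ratios. In the CLR group the two can point in opposite directions: roughly 1.5–7% of trials at ICC 0.025 and about 0.4–2.5% at ICC 0.01. These ranges assume 60–72 practices and depend on the distribution of follow-up, the timing of cases, the form and size of practice effects, and the reading of the period weights, none of which the SAP fully fixes. In the PLR group the problem is negligible. The benefit of a change is mainly a condition that agrees with the reported estimate and does not depend on follow-up balance between arms.

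**What to change.** In 3.3, replace the explanatory clause with: *i.e. the point estimate of the 12-month rate ratio from each group's 7.1.1.1 primary model is above 1 in both the CLR and the PLR group (regardless of significance)*. In 7.1.1, refer to that definition instead of restating the condition.

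Three things should be done first:
- settle the period weights and the averaging scale of the 12-month rate ratio;
- confirm that the PLR regression yields the same 12-month quantity, since 7.1.1.1 describes two periods there but a single rate ratio;
- check the wording against the MHRA communication cited in 3.3.

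Otherwise the cost is one sentence and one cross-reference. It needs no new data and no additional model, and disagreement between the condition and the reported result becomes zero by construction.

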3.4 Treatment assignment and treatment groups

Participants in the study were selected by an automated search in GP databases followed by a manual review of their records. All study subjects received an introductory letter to the study, allowing them 14 days to opt out of anonymised data collection. Following this, GP practices (for the CLR group) or participants (for the PLR group) were randomised to either receiving an invitation to the Cytosponge™ test or to usual care.

Non-responders of invitation to the Cytosponge™ were managed as were the patients in the usual care arm.

Participants with a positive Cytosponge™ result were invited to a **confirmatory endoscopy**. Negative Cytosponge™ patients were subsequently managed as were patients in the usual care arm.

Note: A small sample of patients in the usual care arm and negative Cytosponge™ patients were invited to a **research endoscopy** after the end of their follow-up period. The result of their research endoscopy is *not* part of the primary endpoint analysis. A handful of patients invited to the test were also invited to have a research

BEST3 SOP 008 – BEST3 Statistical Analysis Plan v1.0. [If this SAP has been printed or saved electronically, please check Sharepoint to ensure this version is the most up-to-date.](#)

endoscopy at the beginning of the roll-out of the procedure, but invitations to that group were stopped shortly thereafter, and any research endoscopy results in this group of patients will not be taken into account for any analyses.

4. Patient disposition

4.1 Compliance to the Cytosponge™-TFF3 test

Compliance to test (intervention arm) will be defined on two aspects: attendance and successful swallows.

Participants will be provided with two opportunities to successfully swallow the device. A participant will be considered as having had the Cytosponge™ test if he or she has at least one successful swallow. Attenders will include patients who successfully swallow a sponge and those who present at their appointment but are not able to produce a successful swallow.

Study subjects successfully swallowing a Cytosponge™ may produce a sample deemed inadequate because of processing/technical failures or because the test result is considered to be low-confidence negative (squamous cells only) or equivocal (squamous and glandular cells with equivocal TFF3 staining). These patients will be invited to a repeat Cytosponge™ test.

The following numbers and proportions on compliance will feed into the Trial flowchart (see Figure 2):

- responders: overall, to first invitation letter only, to second invitation letter only
- interested and not interested (out of all responders)
- received screening phone call (out of interested): eligible, ineligible
- attenders and non-attenders/withdrawn (out of eligible)
- produced a successful swallow and unable to swallow (out of attenders)
- 'inadequate' samples (out of successful swallows) at first attempt and at repeat test: processing/technical failures, low-confidence negative (squamous cells only), equivocal (squamous and glandular cells with equivocal TFF3 staining)
- participants with 'inadequate' samples invited for a repeat test, attending the test, producing a successful swallow or unable to swallow
- 'adequate' samples (out of successful swallows) at first attempt, at repeat test, overall (i.e. only repeat test counts for participants having two tests) and in total (i.e. all tests counts): negative (squamous and glandular cells), low-confidence positive (squamous and glandular cells with IM), high-confidence positive (squamous and glandular cells with IM and cellular atypia)

Time from first invitation letter to response will be analysed with a Kaplan-Meier estimate, where the event is "responding to the invite" and survival is "not responding to the invite". However, it should be noted that, in a handful of cases when patients replied very late (> 1 month after invitation) to their test invite, the nurse was not able to offer an appointment (because the study was no longer working in the area) and the patient was marked as a non-responder.

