- Inadequacy rate = proportion of Cytosponge™ test results that are deemed insufficient/inadequate due to processing or technical failure, low-confidence negative (squamous cells only) or equivocal (squamous and glandular cells with equivocal TFF3 staining), to be reported with number of.
- Number and proportion of Cytosponge™ test results deemed insufficient/inadequate due to technical failure only
- Number and proportion of Cytosponge™ test results deemed low-confidence negative only
- Number and proportion of Cytosponge™ test results deemed equivocal only

The above measures will also be presented for first test only and for first and repeat test combined, excluding those patients receiving an inadequate test result but not attending their repeat test.

- 7) Endoscopy referral rates for 'adequate' test results and successful Cytosponge™ swallows:
- Proportion of positive Cytosponge™ patients out of all the ones with an adequate test result, both for first test only, and for first and repeat test combined
 - Proportion of positive Cytosponge™ patients out of all patients swallowing successfully a Cytosponge™ test, both for first test only, and for first and repeat test combined
- 8) Patient acceptability of Cytosponge™:

At first test:

- Number/proportion of patients invited who show interest
- Number/proportion of patients invited who receive screening phone call and how many of these are not eligible to have the test
- Willingness to have the test: number/proportion of patients invited who attend appointment
- Number/proportion of patients who fail to swallow
- Number of attempts to swallow per patient

At repeat test (in case of an 'inadequate' result at first test):

- Number/proportion of patients with an 'inadequate' first test result invited to a repeat test
- Number/proportion of patients with an 'inadequate' first test result interested or not interested in a repeat test
- Willingness to have repeat procedure: number/proportion of patients with an 'inadequate' test result who attend a second appointment
- Number/proportion of patients who fail to swallow
- Number of attempts to swallow per patient

All of these figures for first and repeat tests will be presented in a flowchart similar to the one used for the open Data Monitoring Committee (DMC) reports (see Section 10 for reference).

At baseline (before first test):

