7.1.2 Analysis of secondary endpoints

For the sake of simplicity, the cluster design of part of the Trial will be ignored for the analysis of secondary endpoints.

Any endpoints using data on BE diagnoses will rely on *actual* data available from the Trial, i.e. the methods used for data collection for the primary endpoint will not apply.

The analysis of the secondary endpoints will be further detailed in a separate supplementary SAP.

Using data from the intervention arm *only*:

- 1) Diagnostic accuracy of the Cytosponge™ according to endoscopic findings:
PPVs will be presented with 95% Clopper-Pearson (exact) confidence intervals overall, by age group/sex, by duration of acid-suppressant medication prescriptions prior to baseline and by number of columnal cells present on the sponge.
In Stata, these can be calculated using the command `diagt` or `diagti`. In R, the function `epi.tests` should be used.
- 2) Diagnostic accuracy of the Cytosponge™ test according to endoscopic and pathology findings, i.e. by score of BE severity:
PPV will be presented with a 95% exact confidence interval.
- 3) Performance of Cytosponge™ in detecting IM of the gastric cardia:
PPV will be presented with a 95% exact confidence interval.
- 4) Performance of Cytosponge™ in detecting BE or IM of the gastric cardia:
PPV will be presented with a 95% exact confidence interval.
- 5) Performance of Cytosponge™ in detecting EAC and gastric cancer:
PPV will be presented with a 95% exact confidence interval;
Numbers needed to examine (by Cytosponge™) to detect one OAC or one HGDB will also be calculated.
- 6) Sampling adequacy:
Inadequacy rate will be presented with a 95% exact confidence interval.
- 7) Endoscopy referral rates for adequate test results and successful Cytosponge™ swallows:
The two proportions will be presented with a 95% exact confidence interval.
- 8) Patient acceptability of Cytosponge™:
Proportions will be presented with a 95% exact confidence interval.
Median number of attempts to swallow per patient will be presented with interquartile range (IQR) and range.
At baseline:
 - Measures will be presented with median, IQR and range*At day 7-14:*
 - Measures will be presented with median, IQR and range
 - Differences in STAI-6 scores at day 7-14 and baseline will be compared with a Wilcoxon signed-rank test.
- 9) Physician/nurse acceptability of Cytosponge™: qualitative outcome.
- 10) Safety of Cytosponge™:

See Section 8.

11) Performance of repeat Cytosponge™ test:

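### With two swallow opportunities per test, the median, IQR and range of attempts look the same for any non-zero second-attempt share below about 25%; proportions by attempt would be more informative

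*SAP*

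**What the plan says.** Three parts of the SAP bear on this point.

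- **Limit on attempts (section 4.1).** "Participants will be provided with two opportunities to successfully swallow the device". A participant with at least one successful swallow counts as having had the test.
- **Measures (section 2.3, patient acceptability).** "Number of attempts to swallow per patient" is listed twice, once for the first test and once for the repeat test. Beside it, also at both tests, stands "Number/proportion of patients who fail to swallow".
- **Summary statistics (section 7.1.2, item 8).** For the acceptability measures, "proportions will be presented with a 95% exact confidence interval". The attempts are treated differently: "Median number of attempts to swallow per patient will be presented with interquartile range (IQR) and range".

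Two further statements concern where results will appear. Section 2.3 takes a flowchart from the monitoring committee's open reports as its model: "All of these figures for first and repeat tests will be presented in a flowchart similar to the one used for the open Data Monitoring". Section 7.1.2 says "The analysis of the secondary endpoints will be further detailed in a separate supplementary SAP". The flowchart list in section 4.1 divides attenders into those with a successful swallow and those unable to swallow. It does not divide the successes by attempt.

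**The concern.** Quartiles and range suit a count that spreads over many values. Here, at each test, a patient who tries to swallow makes one attempt or two. On a two-valued variable the median and quartiles move only when the share at the higher value crosses a quarter, a half or three quarters. The range shows only whether both values occur.

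Failure to swallow already has its own measure. What the attempts measure can add is how many patients needed a second try, and the chosen statistics respond poorly to that. The value 2 is also ambiguous, because it covers patients who succeeded second time and patients who failed twice.

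At stake is the descriptive content of one acceptability measure, at the first and the repeat test. No test, comparison between arms or decision depends on it.

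**Working it through.** The SAP states no figure for swallow attempts, so there is none to reproduce.

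**Inputs**
- Values the variable can take: 1 or 2 (section 4.1, read per test).
- Statistics: median, IQR, range (section 7.1.2, item 8).
- Share *p* of patients with two attempts: not given, so an assumption, varied from 0% to 76%.
- Number tested, for illustration only: 13,234 recruited (section 2.5.2), half in the intervention arm (1:1, section 2), 24.0% uptake (section 2.5.3). 13,234 / 2 × 0.24 = 1,588.

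**Step 1: the planned summary as a function of *p*.** With a share 1 − *p* at value 1 and *p* at value 2, the lower quartile, median and upper quartile stay at 1 until *p* reaches about 75%, 50% and 25% respectively. The range is 1-2 as soon as one patient has two attempts and at least one has a single attempt. In a sample of 1,588:

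| Share with two attempts | Median | IQR | Range |
|---|---|---|---|
| 0% | 1 | 1-1 | 1-1 |
| 1%, 5%, 10%, 15%, 20%, 24%, 24.9% | 1 | 1-1 | 1-2 |
| 25% | 1 | 1-1.25 | 1-2 |
| 26% to 49% | 1 | 1-2 | 1-2 |
| 50% | 1.5 | 1-2 | 1-2 |
| 51% to 74% | 2 | 1-2 | 1-2 |
| 76% | 2 | 2-2 | 1-2 |

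The thresholds depend on *p*, not on the number tested, so the same holds at the smaller repeat test. Exactly at a threshold the value depends on the quartile definition used.

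**Step 2: what a proportion would show.** Clopper-Pearson 95% intervals for the share needing a second attempt, n = 1,588:

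| Share | Patients | Exact 95% interval | Planned summary |
|---|---|---|---|
| 1% | 16 | 0.6% to 1.6% | 1 (1-1), 1-2 |
| 5% | 79 | 4.0% to 6.2% | 1 (1-1), 1-2 |
| 10% | 159 | 8.6% to 11.6% | 1 (1-1), 1-2 |
| 20% | 318 | 18.1% to 22.1% | 1 (1-1), 1-2 |
| 24% | 381 | 21.9% to 26.2% | 1 (1-1), 1-2 |

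The data could tell 1% from 10% or 20% with ease. The planned summary prints the same line for all five.

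**Step 3: is the split specified elsewhere in this SAP?** Section 2.3 gives the number and proportion who fail to swallow. Section 4.1 gives success against inability among attenders. The words about a first attempt later in the 4.1 list are paired with the repeat test and concern sample adequacy, so they mean the first test and not the first swallow. No line specifies the proportion who swallowed first time or only second time.

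**The case against.** A reader might infer three stronger things. The SAP does not support any of them.

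- *That the trial could not show how hard the device is to swallow.* The failure proportion is planned with an exact interval at both tests, and section 2.3 also plans a visual analogue scale and an 18-item satisfaction inventory for test experience. Only the split of successes by attempt is missing.
- *That the result is fixed in advance.* It is fixed only if the second-attempt share lies above 0% and below about 25%. The summary differs at 0% and changes again from about 25% upward. The SAP gives no rate that places the trial in the insensitive range, and the shares used above are illustrations.
- *That first-try success will be reported nowhere.* Section 2.3 sends all the listed figures, including attempts, to a flowchart modelled on one that is not at hand, and a flowchart may well show counts. The supplementary SAP may add detail. Neither can be checked. What can be said is that this SAP names a statistic for attempts and does not specify the split.

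The two-valued premise is also a reading of the text. Section 4.1 speaks of two opportunities without saying whether that is per appointment. Per test is the natural reading, since attempts are listed separately for each test. A patient with a repeat test could make more than two attempts in total, but that does not rescue a summary made test by test.

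Finally, median, IQR and range are a conventional default for a count, and no passage contradicts another. That stands: this is a weak choice of statistic, not an error.

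**Conclusion.** The point holds in a limited form. On the per-test reading, the statistics named in section 7.1.2 item 8 cannot separate a 1% from a 24% second-attempt share, and the value 2 mixes late successes with failures. The information lost is the split of successful swallowers by attempt. Failure to swallow remains properly covered.

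This rests on two assumptions: that two opportunities means at most two attempts at each test, and that the true second-attempt share is above zero and below about 25%. From about 25% upward the summary does move, but it takes only a few forms over the whole range.

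The weakness is minor and descriptive and has no effect on the primary endpoint. It is best labelled a free improvement.

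**What to change.** In section 7.1.2 item 8, replace or supplement the median, IQR and range of attempts. Report the number and proportion, each with an exact 95% interval, of patients who:

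1. swallowed at the first attempt;
2. swallowed only at the second attempt;
3. did not swallow.

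The denominator should be all who attempted, separately for the first and the repeat test. Add the first two categories to the flowchart list in section 4.1. If the supplementary SAP already specifies this split, a cross-reference is enough.

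The cost is a sentence in 7.1.2 and a line in 4.1. The SAP already plans to use both the number of attempts and the swallow outcome, and item 8 already applies exact intervals to the other acceptability proportions. No new variable and no change to trial procedures is needed.
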